4. LIST OF ABBREVIATIONS AND DEFINITIONS OF TERMS

The following abbreviations and specialist terms are used in this study protocol.

Table 2: Abbreviations and Specialist Terms

Abbreviation or Specialist Term	Explanation
ADL	Activities of daily living
AE	Adverse event
AESI	Adverse event of special interest
Ag/Ab	Antigen/Antibody
Alb	Albumin
ALP	Alkaline phosphatase
ALT	Alanine aminotransferase
aPTT	Activated Partial Thromboplastin Time
AST	Aspartate aminotransferase
ATC	Anatomical therapeutic chemical
BASO	Basophils
BMI	Body mass index
CI	Confidence interval
CREAT	Creatinine
CSR	Clinical study report
CTCAE	Common Terminology Criteria for Adverse Events
ECG	Electrocardiogram
eCRF	Electronic case report form
eGFR	estimated glomerular filtration rate
EOS	End of Study
ESN	Eosinophils
ET	Early termination
FDA	Food and Drug Administration
FSH	Follicle-stimulating hormone
GCP	Good Clinical Practice
GMP	Good Manufacturing Practice
Hb	Hemoglobin
HbA1c	Hemoglobin A1c
HBsAg	Hepatitis B surface antigen

Abbreviation or Specialist Term	Explanation
HBV	Hepatitis B virus
Hct	Hematocrit
HCV	Hepatitis C virus
HDL-C	High-density lipoprotein cholesterol
HIFU	High intensity focused ultrasound
HIV	Human immunodeficiency virus
IB	Investigator's Brochure
ICF	Informed Consent Form
ICH	International Council on Harmonisation
IEC	Independent Ethics Committee
INR	International Normalized Ratio
IP	Investigational product
IRB	Institutional Review Board
ISR	Injection site reaction
IUD	Intrauterine device
IUS	Intrauterine hormone-releasing system
LDL-C	Low-density lipoprotein cholesterol
LLLT	Low-level laser therapy
LYM	Lymphocytes
MCHC	Mean corpuscular hemoglobin
MCV	Mean corpuscular volume
MedDRA	Medical Dictionary for Regulatory Activities
MM	Medical Monitor
MONO	Monocytes
NEUT	Neutrophils
NHMRC	National Health and Medical Research Council
OTC	Over-the-counter
PK	Pharmacokinetics
PLAT	Platelets
PT	Preferred term
RBC	Red blood cells/ erythrocytes
SAD	Single ascending dose

Abbreviation or Specialist Term	Explanation
SAE	Serious adverse event
SAP	Statistical analysis plan
SD	Standard deviation
SOC	System organ class
TBIL	Total bilirubin
TEAE	Treatment-emergent adverse event
TGA	Therapeutic Goods Administration
U	Urea
ULN	Upper limit of normal
US	United States
WBC	White blood cells
WHO	World Health Organization
WOCBP	Woman of childbearing potential
β-hCG	Beta human chorionic gonadotropin

Definitions of the pharmacokinetic parameters to be determined are provided in [Table 10](#).

6. BACKGROUND AND INTRODUCTION

6.1. Introduction

The focus on body aesthetics and appearance continues to influence the treatment-seeking behavior of many people in modern society. The most popular body contouring approaches used to improve the cosmesis of subcutaneous fat deposits are surgical and include liposuction, abdominoplasty, and thigh lifts, among other procedures. This increasing demand has led to the rapid growth and development of noninvasive, non-surgical treatment techniques. Although surgical techniques can result in the most pronounced outcomes in respect to improved body contouring results, they are also associated with inherent risk and complications such as pain, swelling, prolonged recovery, scarring, hematoma or infection, which make noninvasive procedures increasingly popular ([Adatto 2014](#); [Kennedy 2015](#)).

The risks, financial costs and lengthy downtime associated with surgical procedures for fat reduction have led to the development of noninvasive techniques ([Kennedy 2015](#)). In recent years, noninvasive body contouring techniques have become one of the most widespread procedures and are growing fast in areas of esthetic medicine ([Nestor 2013](#)). Noninvasive treatment approaches are painless, safe, and require little to no downtime ([Adatto 2014](#)).

Commonly used treatment options for abdominal and thigh subcutaneous fat have been limited to invasive surgical or non-surgical procedures. Lipoplasty was the most popular procedure performed by American Society of Aesthetic Plastic Surgery members in 2020, with 296,601 procedures performed ([ASAPS 2020](#)). Unfortunately, surgical liposuction under general anesthesia carries significant potential risk and complications to a person seeking an aesthetic improvement; 2 independent surveys of board-certified aesthetic plastic surgeons in the United States (US) determined the mortality rate to be approximately 20 deaths per 100,000 procedures ([Grazer 2000](#)).

As for non-surgical procedures, there are now numerous options for fat reduction which utilize medical devices to deliver certain frequency of energy or cold temperature through the skin to ablate subcutaneous fat cells in the anterior abdomen, such as radiofrequency, high intensity focused ultrasound (HIFU), cryolipolysis or low-level laser therapy (LLLT) ([Friedmann 2015](#)). In many cases (e.g., cryolipolysis, HIFU), these non-surgical procedures also cause inflammation which is related to the mechanism of removing the ablated fat cells from the treated area ([Jalilian 2012](#)). This inflammatory process may result in pain, swelling and redness along with the increased recovery time for the process to complete and time to view aesthetic benefit. In addition, the cost of these devices as well as the disposables required must be taken into consideration for each treatment.

There is another non-surgical treatment for reducing subcutaneous fat which is known as mesotherapy or lipodissolve, a minimally invasive procedure. Mesotherapy involves a series of injections of medications that are purported to melt away localized fat deposits. Combinations of drugs such as phosphatidylcholine and deoxycholate, deoxycholate alone or combinations including other drugs or products such as vitamins, minerals, and herbal extracts may be used ([Rotunda 2006](#); [Atiyeh 2008](#)). However, warning letters were issued by the Food and Drug Administration (FDA) to medical spas offering mesotherapy for unfounded claims of efficacy ([Atiyeh 2008](#); [Duncan 2011](#)). There were also numerous reports of significant adverse events

(AEs) (e.g., skin necrosis, infections, etc.) due to unregulated mesotherapy ([Atiyeh 2008](#), [Duncan 2011](#)). This creates an unmet medical need to develop an injectable alternative with promising efficacy and an acceptable safety profile to fulfill the need of reducing abdominal and thigh subcutaneous fat.

CBL-514 injection (CBL-514), is a new injection for lipolysis product developed by Caliway Biopharmaceuticals Co., Ltd. The product is supplied in a 20 mL glass vial with a stopper. Each milliliter of CBL-514 contains [REDACTED] the drug substance, the CBL-514 powder, with [REDACTED] curcumin (CAS number: 458-37-7) and [REDACTED] *trans*-resveratrol (CAS number: 501-36-0) serving as the active pharmaceutical ingredients. CBL-514 is compatible to use with needle and syringe for subcutaneous injection. CBL-514 has shown promising efficacy and safety profiles in prior research in in vitro and animal models for the proposed indication in promoting adipose cell apoptosis.

6.2. Summary of Nonclinical and Clinical Studies

6.2.1. Nonclinical Studies

CBL-514 has undergone an extensive nonclinical safety and efficacy evaluation. These nonclinical studies conducted for CBL-514 are described in detail in the CBL-514 Investigator's Brochure (IB).

6.2.2. Clinical Studies

The safety and tolerability of injection lipolysis with CBL-514, pharmacokinetic (PK) profile of and preliminary efficacy of repeated doses of CBL-514 in reducing abdominal subcutaneous fat at the target area has been evaluated in a first-in-human Phase 1/2a study (CBL-16001) in Australia.

In the Phase 1 component of CBL-16001, CBL-514 was assessed for safety and tolerability, and the PK profile was evaluated. The study was conducted with a single ascending dose (SAD) design, in 9 sequential cohorts (Cohorts 1 to 9). The CBL-514 dose levels assessed were 2, 10, and 20 mg at 0.5 mg/cm²; 40 mg at 1.0 mg/cm²; and 40, 80, 160, 240, and 320 mg at 2.0 mg/cm². For Cohorts 1 to 5, both CBL-514 and placebo groups were administered on each side of abdomen in a blinded manner to evaluate the possible AEs attributed to the components of CBL-514. For Cohorts 6 to 9, only CBL-514 was dosed in participants.

In the Phase 2a component of the CBL-16001 study, the safety and efficacy of multiple injections of CBL-514 for reducing abdominal subcutaneous fat was assessed. There were 3 parallel treatment groups. The CBL-514 dose levels assessed were CBL-514 180 mg at 1.2 mg/cm², 240 mg at 1.6 mg/cm², and 300 mg at 2.0 mg/cm². Each enrolled Phase 2a participant received 4 courses of study drug, 1 course of CBL-514 every 2 weeks, over a period of 6 weeks.

6.2.2.1. Safety and Tolerability

Overall, single doses of CBL-514 were well tolerated through the ascending dose escalation scheme from 2 to 320 mg in the Phase 1 portion of CBL-16001 study. The results for physical examination, vital signs, ECG, and laboratory tests, including biochemistry, hematology, coagulation, and urinalysis, all showed favorable profiles for the safety of CBL-514. While there

were no systemic treatment-emergent AEs (TEAEs) from CBL-514, the most frequent TEAEs were injection site reactions (ISRs). In Cohorts 1 to 5, the drug-related ISRs were warmth (81%), erythema (75%), bruising (63%), yellow discoloration (38%), tenderness (31%), and pruritus (25%), with higher incidence on the treatment area. All drug-related ISRs were graded as mild and most resolved within 8 days; bruising resolved within the 28-day follow-up period. There was no apparent difference in severity or duration of common ISRs with dose escalation.

Within the first 5 cohorts (Cohort 1 to 5) which received both placebo and CBL-514, 50% of participants in the pooled placebo group and 81% of participants in the pooled CBL-514 group experienced at least 1 ISR. In Cohorts 6 to 9, the most frequently occurring CBL-514 related ISRs were erythema, warmth, bruising, swelling, and yellow discoloration (reported for 80% to 99% of participants), tenderness and pruritus (reported for 60% to 79% of participants), and pain (reported for 50% of participants). All CBL-514-related ISRs were graded as mild to moderate. Among these ISRs, yellow discoloration was caused by the natural yellow pigment, curcumin, an active component of CBL-514. In all cases, the yellow discoloration faded away and completely disappeared from the skin within 8 days (for further details, refer to the IB).

Overall, CBL-514 appeared to be safe and well tolerated when administered as multiple doses at 180 to 300 mg in the Phase 2 portion of the CBL-16001 study. The most commonly reported treatment-related TEAEs were injection site bruising (100%), injection site erythema (100%), injection site pain (100%), injection site swelling (100%), injection site pruritus (95.3%), injection site warmth (90.7%), injection site discoloration (79.1%), and injection site induration (46.5%). The majority of TEAEs were either mild or moderate in severity. There were no apparent differences between the different CBL-514 dosing groups in terms of study treatment-related TEAEs.

6.2.2.2. Pharmacokinetics

PK data were collected in the Phase 1 portion the CBL-16001 study for participants in Cohorts 3 through Cohort 9 (single doses of CBL-514, from 20 to 320 mg).

Curcumin median t_{\max} ranged from approximately 2 to 5 hours while geometric mean curcumin $t_{1/2}$, when estimable, ranged from approximately 2 to 3.5 hours. Curcumin exposure (C_{\max} and $AUC_{0-\text{last}}$) increased in an approximately dose proportional manner with an 8-fold increase in CBL-514 dose from 20 to 160 mg. Following the 2 highest doses, which represent a 12- and 16-fold increase in the dose from 20 mg, geometric C_{\max} increased approximately 15- and 18-fold. The geometric mean $AUC_{0-\text{last}}$ increased on average approximately 16-fold, following each of the top 2 doses. Based on the statistical assessment of curcumin dose proportionality, the increase in curcumin exposure was proportional to curcumin dose across the dose range studied. The 90% confidence interval (CI) for the slope of the relationship between curcumin dose and exposure included 1 for C_{\max} , $AUC_{0-\text{last}}$, and $AUC_{0-\text{inf}}$.

Resveratrol median t_{\max} ranged from 4 to 5 hours while geometric mean resveratrol $t_{1/2}$ ranged from 3 to 5 hours. Resveratrol exposure (C_{\max} and $AUC_{0-\text{last}}$) increased in an approximately dose proportional manner with an 8-fold increase in CBL-514 dose from 20 to 160 mg. Exposure to resveratrol increased following the administration of 240 and 320 mg CBL-514 doses with exposure tending to plateau from 240 to 320 mg of CBL-514. Following the 2 highest doses, which represent a 12- and 16-fold increase in dose from 20 mg, the increase in geometric mean resveratrol C_{\max} was approximately 10-fold for both doses while the increase in geometric mean

resveratrol AUC_{0-last} was approximately 14-fold for both doses. Based on the statistical assessment of resveratrol dose proportionality, the increase in resveratrol C_{max} was slightly less than proportional to resveratrol dose while resveratrol AUC_{0-last} and AUC_{0-inf} was proportional to resveratrol dose. The upper bound of the 90% CI for the slope of the relationship between resveratrol C_{max} and resveratrol dose did not include 1 while the 90% CI for the slope of the relationship between resveratrol AUC_{0-last} and AUC_{0-inf} and resveratrol dose included 1.

6.2.2.3. Efficacy

Four courses of CBL-514 injections at doses of 240 mg and 300 mg showed statistically significant decreases in fat volume and fat thickness compared to Baseline ($p < 0.001$) in the Phase 2 portion of the CBL-16001 study. There was an apparent dose-response effect observed, with CBL-514 injection at multiple doses of 300 mg yielding statistically significant reductions from Baseline in fat volume compared to the lowest dose group.

6.3. Dosage Rationale

In order to cater to a greater range of body shapes and/or levels of fat accumulation, higher doses of CBL-514 may be required to provide effective treatment. On the basis of the favorable safety and efficacy profile demonstrated in the CBL-16001 study, further studies at higher doses are planned to evaluate the efficacy, safety, tolerability and PK of CBL-514 injection for reducing abdominal and thigh subcutaneous fat.

An ongoing Phase 2 study (protocol number: CBL-0202) has an integrated design consisting of a SAD part in Stage 1, followed by a parallel-arm, placebo-controlled design in Stage 2. The doses being evaluated in Stage 1 are 320, 480, 640, and 800 mg at 2.0 mg/cm². In Stage 2, the planned minimum dose is 300 mg and the planned maximum dose is 600 mg. The dose adjustment will depend on the level of fat accumulation on a participant's abdomen at the discretion of the Investigator. The dose for Stage 2 is to be confirmed or adjusted after an interim safety report has been reviewed by the Institutional Review Board/Independent Ethics Committee (IRB/IEC).

The PK profile of curcumin and resveratrol has been investigated following subcutaneous administration CBL-514 at doses up to 320 mg. The present study, CBL-0203, is intended to evaluate the PK profile of curcumin and resveratrol at the maximal CBL-514 dose. The maximal dose is anticipated to be 800 mg at 2.0 mg/cm², based on the emerging safety profile in Stage 1 of the ongoing CBL-0202 study. The dose for CBL-0203 is to be confirmed or adjusted after an interim safety report from CBL-0202 has been reviewed by the IRB/IEC.

6.4. Participant Population

The study will be conducted in healthy male and female volunteers aged 18 to 64 years (inclusive at the time of informed consent) with a subcutaneous fat thickness of at least 3.00 cm (30.0 mm) measured by caliper skinfold method, surrounding the center of localized area of treatment as well as the left and right edges of treatment area at Screening and Day 1.

Women of childbearing potential (WOCBP) will be included and are subject to contraceptive requirements during the study from Screening until study completion, including the follow-up period, and for at least 90 days after the last dose of investigational product (IP) (see [Section 9.1](#)). WOCBP must demonstrate negative pregnancy testing at Screening and before

administration of IP. This is in line with regulatory Guidance on Nonclinical Safety Studies for the Conduct of Human Clinical Trials and Marketing Authorization for Pharmaceuticals (FDA 2006).

6.5. Summary of Potential Risks and Benefits

Participants may or may not receive direct benefit from participating in this study. To date, the nonclinical and clinical study data suggest that subcutaneous administration of CBL-514 may be effective in reducing subcutaneous fat in humans.

Clinical data has demonstrated that CBL-514 is well tolerated at doses from 2 to 320 mg, and an ongoing clinical study aims to investigate the safety and tolerability of CBL-514 at doses up to and including the maximal dose. The dose to be used in this study will be confirmed or adjusted after an interim safety report from CBL-0202 has been reviewed by the IRB/IEC, reducing the likelihood of unforeseen risks for study participants.

6.6. Ethical Principles

This study will be conducted in accordance with the principles of the current Declaration of Helsinki (Ethical Principles for Medical Research Involving Human Subjects) and with the NHMRC National Statement on Ethical Conduct in Human Research 2007 (updated 2018). The conduct of the study will be in accordance with the ICH Integrated Addendum to E6(R1): Guideline for GCP ICH E6(R2).

This study will be conducted under a protocol reviewed and approved by an IRB/IEC and investigations will be undertaken by scientifically and medically qualified persons; where the benefits of the study are in proportion to the risks.

7. TRIAL OBJECTIVES AND PURPOSE

7.1. Objectives

7.1.1. Primary Objective

The primary objective of the study is to evaluate the PK profile of the components of CBL-514 in plasma following administration of CBL-514 into subcutaneous fat.

7.1.2. Secondary Objective

The secondary objectives of the study are to:

- Identify and assess the metabolites of CBL-514 in plasma following administration of CBL-514 into subcutaneous fat.
- Evaluate safety and tolerability of CBL-514 administered into subcutaneous fat.

7.2. Endpoints

7.2.1. Primary Endpoints

The primary endpoints of the study are:

- To evaluate the PK of the components of CBL-514 in plasma following administration of CBL-514 into subcutaneous fat. PK parameters following a single course of administration of CBL-514 will include, but are not limited to the following:
 - Maximum analyte concentration (C_{\max})
 - Time to C_{\max} (t_{\max})
 - Area under the concentration-time curve from time 0 to the last quantifiable concentration (AUC_{0-t})
 - Area under the concentration-time curve from time 0 to 24 hours post-dose (AUC_{0-24hr})
 - Area under the concentration-time curve from time 0 extrapolated to infinity (AUC_{0-inf})
 - Elimination half-life ($t_{1/2}$)
 - Apparent total plasma clearance (CL/F)
 - Apparent terminal volume of distribution (V_z/F)

7.2.2. Secondary Endpoints

The secondary endpoints of the study are:

- To identify and characterize the metabolites of CBL-514 in plasma following administration of CBL-514 into subcutaneous fat.

- Safety and tolerability following a single subcutaneous dose of CBL-514 as assessed by recording of TEAEs, laboratory assessments, vital signs, ECGs, and physical examinations.

8. INVESTIGATIONAL PLAN

8.1. Overall Study Design

This is a Phase 2 study to evaluate the safety, tolerability, PK and metabolite profile of CBL-514 injection at the maximal use dosage.

This Phase 2 study has an open-label and single course design. A total of 10 adult participants, composed of 5 females and 5 males, will be enrolled in a single cohort. Each participant will receive a single course of treatment with CBL-514 800 mg on the abdomen (administered as multiple subcutaneous injections) on Day 1 only.

Each participant will participate in the study for approximately 4 weeks, with a maximum expected duration of 61 days including up to 28 days for screening assessments, an Admission/Baseline visit on Day 1 with an overnight stay until Day 2, and 2 Follow-up visits (2 weeks [in-clinic] and 4 weeks [telephone] post treatment).

A schematic of the study design is provided in [Figure 1](#).

Study visits and assessments will occur as delineated in the Schedule of Assessments presented in [Table 4](#).

8.2. Number of Participants

A total of 10 adult participants, composed of 5 females and 5 males, will be enrolled in a single cohort. The sample size is not based on formal hypothesis testing but is consistent with currently accepted standards for exploratory investigation design.

8.3. Dose Adjustment and Safety Oversight

Administration of the IP should be in accordance with dose scheme. Deviations in administration will potentially affect the evaluation of PK.

Safety oversight will be provided by the Investigator, the Sponsor's Representative and the Medical Monitor (MM) as described in the Medical Monitoring Plan and Safety Management Plan.

If at any time the study is terminated, a written statement fully documenting the reasons for termination will be provided to the relevant IRB/IEC (see [Section 8.5](#)).

8.4. Stopping Criteria

Administration of the IP may be paused, and additional participants will not receive IP, until a consultation has taken place between the Investigator, the MM, and the Sponsor representative under the following circumstances:

1. Any participant experiences an AE as Grade 3 (as defined in the NCI-CTCAE Version 5.0) for cardiovascular, renal or hepatic events considered to be at least possibly related to IP.
2. Except for cardiovascular, renal or hepatic events specified in Criterion #1, any participant experiences an AE as Grade 4 and considered to be at least possibly related to IP.

3. Any participant experiences a serious AE (SAE) that is considered to be at least possibly related to the IP.
4. An AE or group of AEs that singularly or in aggregate suggests to the Investigator or Sponsor that the IP is poorly tolerated and further treatment per protocol may not be safe.

If any of these criteria are met, consultation between the Sponsor representative, the Investigator, and the MM will take place as soon as possible to evaluate the event. Participants should remain in the study and be followed until the AE resolves or stabilizes.

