14.2.1.1. Severity of an Adverse Event

Severity of AEs will be assessed by the Investigator according to the CTCAE, Version 5.0; please refer to [Table 8](#).

Table 8: CTCAE Severity Grade Description

Grade 1	Mild	Asymptomatic or mild symptoms; clinical or diagnostic observations only; intervention not indicated.
Grade 2	Moderate	Minimal, local or noninvasive intervention indicated; limiting age-appropriate instrumental ADL*.
Grade 3	Severe	Severe or medically significant but not immediately life-threatening; hospitalization or prolongation of hospitalization indicated; disabling; limiting self-care ADL**. Note: An experience may be severe but may not be serious (e.g., severe headache).
Grade 4	Life-Threatening	Life-threatening consequences; urgent intervention indicated.
Grade 5	Fatal	Death related to AE.

Abbreviations: ADL = Activities of daily living.

Notes: A semi-colon indicates 'or' within the description of the grade.

*Instrumental ADL refer to preparing meals, shopping for groceries or clothes, using the telephone, managing money, etc.

**Self-care ADL refer to bathing, dressing and undressing, feeding self, using the toilet, taking medications, and not bedridden.

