14.2.3. Definition of Serious Adverse Event

An SAE is an AE occurring during any study phase (i.e., Baseline, treatment, or Follow-up), and at any dose of the IP, that fulfills one or more of the following:

- Results in death
- It is immediately life-threatening
- It requires in-patient hospitalization or prolongation of existing hospitalization
- It results in persistent or significant disability or incapacity
- Results in a congenital abnormality or birth defect
- It is an important medical event that may jeopardize the participant or may require medical intervention to prevent one of the outcomes listed above

Important medical events that may not be one of the above may be considered an SAE by the Investigator when, based upon appropriate medical judgment, they are considered clinically significant and may jeopardize the participant, or may require medical or surgical intervention to prevent one of the outcomes listed above.

An AE is considered “life-threatening” if, in the opinion of either the Investigator or the Sponsor, its occurrence places the participant at immediate risk of death. It does not include an AE that, had it occurred in a more severe form, might have caused death.

Notes:

*Medical and scientific judgement should be exercised in deciding whether and adverse event/ reaction should be classified as serious in other situations.

*If the participant requires emergency department admission only or undergoes elective surgical treatments will not be considered an SAE.

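### Section 8.4 as worded: a related, non-serious Grade 4 cardiovascular, renal or hepatic event meets neither Criterion 1 nor Criterion 2, although the same event at Grade 3 meets Criterion 1

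*Combined protocol and SAP*

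**What the plan says.** Protocol Section 8.4 gives the consequence first: "Administration of the IP may be paused, and additional participants will not receive IP, until a consultation has taken place". It adds that a consultation follows as soon as possible once any criterion is met. The four criteria are:

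- Criterion 1: "Any participant experiences an AE as Grade 3 (as defined in the NCI-CTCAE Version 5.0) for cardiovascular, renal or hepatic events", when at least possibly related to the investigational product (IP).
- Criterion 2: "Except for cardiovascular, renal or hepatic events specified in Criterion #1, any participant experiences an AE as Grade 4", with the same relatedness condition.
- Criterion 3: "Any participant experiences a serious AE (SAE) that is considered to be at least possibly related to the IP".
- Criterion 4: "An AE or group of AEs that singularly or in aggregate suggests to the Investigator or Sponsor that the IP is poorly tolerated", so that further treatment may not be safe.

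Three other places bear on how these work. Table 8 (Section 14.2.1.1) describes Grade 4 as "Life-threatening consequences; urgent intervention indicated", and its footnote says that a semicolon stands for 'or'. Section 14.2.6 says that severity and seriousness are different things. Section 14.2.3 lists the seriousness criteria, any one of which is enough, and then adds a note: "If the participant requires emergency department admission only or undergoes elective surgical treatments will not be considered an SAE".

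**The concern.** Section 8.4 singles out three organ systems for a trigger at a lower grade than elsewhere. One would expect the trigger to hold at every grade above that. As worded it does not: Criterion 1 stops at the grade it names, and Criterion 2 hands the same organ systems back to Criterion 1. A worse event can then fail to start a consultation that a milder one would start.

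What is at stake is whether participants not yet dosed receive 800 mg before the Investigator, the Medical Monitor and the Sponsor have conferred. A defined trigger takes that step out of individual discretion. Criterion 4 puts it back.

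The Section 14.2.3 note is a second, separate matter. SAE status drives Criterion 3, the 24-hour reporting in Section 14.2.4 and the SAE summary in Section 16.4.1. A note that removed SAE status from an event meeting another seriousness criterion would affect all three.

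**Working it through.** There is no figure in the plan to reproduce. The sample size rests on no hypothesis test (Section 16.1) and no event rate is attached to the stopping criteria. The check is one of logic.

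**Step 1. Apply Criteria 1 to 3 literally to a related event.**

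| Related event | Criterion 1 | Criterion 2 | Criterion 3 |
|---|---|---|---|
| Cardiovascular, renal or hepatic, Grade 3, not an SAE | met | not met | not met |
| Cardiovascular, renal or hepatic, Grade 4, not an SAE | not met | not met | not met |
| Cardiovascular, renal or hepatic, Grade 4, SAE | not met | not met | met |
| Cardiovascular, renal or hepatic, Grade 5 | not met | not met | met (death is an SAE) |
| Other system, Grade 4, not an SAE | not met | met | not met |

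The second row is the gap: no defined trigger fires, and only Criterion 4 is left.

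**Step 2. Can a Grade 4 event be non-serious under this protocol?** Yes. Because the semicolon in Table 8 means 'or', an indication for urgent intervention alone is enough for Grade 4. The life-threatening seriousness criterion needs an immediate risk of death, and the important-medical-event criterion rests on the Investigator's judgement. Section 14.2.6 keeps grade and seriousness apart. Laboratory findings show a possible route: under Section 14.2.5 a clinically significant abnormality can be an AE without symptoms and is an SAE only if it meets a seriousness criterion, and the biochemistry panel in Section 14.1.7.2 includes renal and hepatic markers. How often this would happen cannot be derived, because the event-specific CTCAE grades are not in the documents.

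**Step 3. Does the gap survive other readings?** Three wordings can each be read in two ways, giving 2 × 2 × 2 = 8 combinations:

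- Criterion 1: exactly Grade 3, or Grade 3 and above.
- Exception in Criterion 2: the three organ systems as a class, or only their Grade 3 events.
- Section 14.2.3 note: overrides every seriousness criterion except death, or qualifies hospitalization only.

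| Criterion 1 | Exception | Note overrides | Note qualifies hospitalization only |
|---|---|---|---|
| Exactly Grade 3 | Organ class | Gap | Gap, narrower |
| Exactly Grade 3 | Grade 3 events only | No gap | No gap |
| Grade 3 and above | Organ class | No gap | No gap |
| Grade 3 and above | Grade 3 events only | No gap | No gap |

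The gap appears in 2 of 8 combinations, both keeping the literal wording of Criteria 1 and 2. This counts readings; it is not a probability.

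**Step 4. What does the note add?** Divide related Grade 4 events in the three systems by whether a seriousness criterion is otherwise met and whether care was in the emergency department only, giving 2 × 2 = 4 types. If the note qualifies hospitalization only, 2 of the 4 escape Criteria 1 to 3: those that meet no seriousness criterion. If it overrides, 3 of the 4 escape: the extra type meets another seriousness criterion but was managed in the emergency department only. The note widens the gap on the broad reading and is not needed for it.

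**Step 5. Which readings does the text favor?** Criterion 1 sets a floor for relatedness in the same sentence and sets none for grade. Limiting the exception in Criterion 2 to Grade 3 events would leave it with nothing to do, since a Grade 3 event is never a Grade 4 event. The wording therefore leans to the literal combination, even if the intention was different.

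**The case against.** The strongest reply is that this is loose drafting. A scheme that sets a lower bar for three organ systems, and then exempts them from the higher bar, is ordinarily understood to cover everything above the lower bar. Read so, the gap vanishes. That is probably the intention, but the words do not say it, and site staff have to apply the words.

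The backstops also carry weight. Many Grade 4 events will be SAEs, because an event that needs urgent intervention will often count as an important medical event. Criterion 4 can be met by a single AE. Section 8.3 gives continuing oversight to the Investigator, the Sponsor's Representative and the Medical Monitor, and Section 8.5 allows suspension at any time. These make an unnoticed event less likely; none of them is a defined trigger. The pause itself is worded permissively, but the consultation is not.

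Three stronger readings are tempting, and the documents do not support them.

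- A reader might infer that fatal events are missed as well, since neither Criterion 1 nor Criterion 2 names Grade 5. Death is a seriousness criterion, so a related fatal event always meets Criterion 3.
- A reader might infer that the emergency department note certainly strips SAE status from any event treated and discharged there. The note sits beside elective surgery, follows a call for medical judgement, and can be read as clarifying hospitalization alone. The broad reading is possible, not established.
- A reader might infer an unreviewed jump in dose, since 800 mg is 800/320 = 2.5 times the highest single dose in the completed study. Sections 6.3 and 6.5 say that CBL-0202 is evaluating doses up to 800 mg and that the dose here is confirmed or adjusted after IRB/IEC review of an interim safety report from that study. That bears on the choice of dose and leaves the wording of Section 8.4 as it is.

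**Conclusion.** Section 8.4 is wrong as written. For three of three named organ systems, the defined triggers lapse between Grade 3 and Grade 4 when the event is related and is not classed as an SAE. Such an event is possible under Table 8 and Section 14.2.6, and only the judgement-based Criterion 4 then covers it. There is no gap at Grade 5 and none at Grade 4 for other organ systems.

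The conclusion assumes that Criterion 1 means the grade it names and that the exception in Criterion 2 covers the organ systems as a class. It does not depend on the emergency department note. The note is a separate ambiguity: read broadly, it conflicts with the seriousness criteria above it and widens the gap; read narrowly, it does neither.

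The practical reach is limited. This is a single-dose study in 10 participants, the rule protects only those not yet dosed, the frequency of such an event is unknown, and the pharmacokinetic analysis is untouched. A safety trigger that reverses with severity still deserves correction, and correcting it is cheap.

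**What to change.** The sponsor should reconcile Criteria 1 and 2 in Section 8.4 with each other, so that the pause trigger does not lapse as severity rises within the three named organ systems. It should also reconcile the emergency department note in Section 14.2.3 with the seriousness criteria listed above it, so that a site can tell what happens to an event that falls under both. Which grades and which clinical rule apply is for the sponsor, the Investigator and the Medical Monitor to settle; none is proposed here.

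The cost is a short wording amendment through the route in Section 22.1, and possibly a few more consultations during the study.
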